## 4 STUDY DESIGN

### 4.1 OVERALL DESIGN

The hypothesis to be studied in this Trial is that criticality in the brain depends on the balance of cortical excitation to inhibition and that sub-criticality impacts on cognitive control and subjective cognitive effort. This hypothesis leads to predictions including that TMS protocols which decrease the cortical excitation to inhibition ratio (like continuous theta burst stimulation) will make the brain more sub-critical while protocols which increase the excitation to inhibition ratio (like intermittent theta burst stimulation) will make the brain more super-critical. In turn, when theta-burst stimulation is targeted at regions involved in oculomotor control like the FEF, changes in brain criticality will alter task performance. Specifically, manipulations which make the brain operate closer to criticality will increase susceptibility and information transfer. These functional consequences will thereby lead to worse, more variable performance on tasks which require stability (like memory-guided saccade tasks), lower switch costs and subjective effort associated with task switching (e.g. between anti- and pro-saccade tasks), and better cognitive control (e.g. anti-saccade response inhibition) resulting from better communication between top-down control regions and lower-level sensorimotor effectors.

We will use a double-blind, sham-controlled, crossover, repeated measures design. Specifically, on different days, separated by at least one week, participants will receive continuous theta burst stimulation (cTBS) or intermittent theta burst stimulation (iTBS) with either active stimulation or sham stimulation to their right frontal eye field (FEF). The order of these sessions is pseudo-randomized across participants. Specifically, 20 of our target 60 participants will be randomly pre-assigned to have sham stimulation on their first session (10 sham iTBS + 10 sham cTBS), 20 will have active cTBS on their first session, and 20 will have active iTBS on their first session. The pre-assignment will be determined by permutation of a list of subject numbers using an assignment algorithm that will be executed by a collaborator who is not directly involved in the study. This collaborator will maintain the blinding codes until de-blinding at the end of the study. Errors in randomization will be documented and session order will be included as a covariate in all analyses.

#### 4.2 SCIENTIFIC RATIONALE FOR STUDY DESIGN

Participants will serve as their own controls in this repeated-measures design. This design is ideal for avoiding random effects of individual differences unrelated to the constructs of interest and will provide maximal power for detected control versus target stimulation effects. All participants will be healthy, young adults. This group is ideal for studying normal brain function apart from developmental effects and aging effects and without any confounding effects of disease or disorder.

#### 4.3 JUSTIFICATION FOR INTERVENTION

There are few tools for causally manipulating the cortical balance of excitation to inhibition in humans. TMS was chosen as an intervention for modulating E/I balance in the frontal eye field to alter critical dynamics with consequences for oculomotor control and subjective cognitive effort. Transcranial magnetic stimulation has already been shown to modulate cortical E/I balance, and separately to modulate oculomotor control when targeting the FEF. It is widely used, safe and effective. While there are pharmacological means of modulating E/I balance, it is impossible to selectively target the FEF with pharmacological interventions.

A single train of 600 pulses of continuous theta burst stimulation (cTBS) or 600 pulses of intermittent theta burst stimulation (iTBS) is a standard design. We are using a modification involving two trains of 600 pulses separated by 5 to 25 minutes of rest in between, based on a meta-analysis showing that the effects are more reliable and more durable for a spaced cTBS and spaced iTBS design relative to a single train designs (Chung et al. 2016).

We will require three separate stimulation sessions for participants so that we can compare the effects of active versus sham stimulation at the FEF. The sessions will be separated by at least one week providing sufficient time to minimize the chances of carry-over effects from one session to the next.

Three sessions are needed for a within-participants comparison of active versus sham stimulation effects.

#### 4.4 END-OF-STUDY DEFINITION

A participant is considered to have completed the study if he or she has completed the MR scan session, one sham stimulation session and two active stimulation sessions.

The end of the study is defined as completion of the third stimulation session as shown in the Schedule of Activities (SoA), **Section 1.3**.

### 5 STUDY POPULATION

#### 5.1 INCLUSION CRITERIA

In order to be eligible to participate in this study, an individual must meet all of the following criteria:

1. Provision of signed and dated informed consent form
2. Stated willingness to comply with all study and availability for the duration of the study
3. Males and females; Ages 18-45
4. Healthy, neurologically normal with no diagnosed mental or physical illness
5. Willingness to adhere to the MRI and two session stimulation protocol
6. Fluent in English
7. Normal or corrected to normal vision
8. At least twelve years of education (high school equivalent)

Participants will report simply whether they meet screening criteria prior to consent and this data will not be retained. We will only retain data collected after participants give signed written consent and are thus considered enrolled in the study. Participants responding that they do not meet one of the screening criteria will not be enrolled.

#### 5.2 EXCLUSION CRITERIA

An individual who meets any of the following criteria will be excluded from participation in this study:

1. Ongoing drug or alcohol abuse
2. Diagnosed psychiatric or mental illness
3. Currently taking psychoactive medication
4. Prior brain injury
5. Metal in body
6. History of seizures or diagnosis of epilepsy
7. Claustrophobia
8. Pregnant or possibly pregnant
9. Younger than 18 or older than 45
10. Use of medications which potentially lower the seizure threshold

Participants younger than 18 are excluded because there is evidence that cortical excitation to inhibition changes throughout childhood and adolescence and has been associated with an increase in critical dynamics with development (Smit et al. 2011). There is also evidence of increasing excitation to inhibition altering scale-free properties linked to critical dynamics in older adults relative to young adults (Voytek et al. 2015). We are restricting our study to young adults aged 18-45 to avoid any confounds associated with early development or cognitive aging.

Participants will be asked if they are pregnant or possibly pregnant and excluded from participation if they affirm either.

### 5.3 LIFESTYLE CONSIDERATIONS

During this study, participants are asked to:

- Come to the study well-rested
- Refrain from using products in their hair to avoid adversely impacting impedance for EEG recordings
- Avoid high amounts of caffeine intake the morning of the study

### 5.4 SCREEN FAILURES

Screen failures are defined as participants who consent to participate in this study but are not subsequently assigned to the study intervention or entered in the study. Individuals who do not meet the criteria for participation in this trial (screen failure) because of meeting one or more exclusion criteria that are likely to change over time may be rescreened. Examples include coming back for a stimulation session after receiving a full night's rest, or without products in the participant's hair.

## 5.5 STRATEGIES FOR RECRUITMENT AND RETENTION

Participants will be recruited via flyers and announcements which detail core inclusion / exclusion criteria. As such we only anticipate needing to recruit around 65 individuals in order to meet our target (60 participants; 30 male / 30 female) recruitment. Flyers will be posted around the Rutgers University Community, and announcements will be posted in local periodicals and digital message boards, which is appropriate for communicating with a sample of young adults in the target age range. This recruitment strategy has proven successful in recruiting participants who match community demographics in prior study and we anticipate it will remain successful going forward.

Potential participants who see our flyers and announcements will be invited to expressing their interest by emailing us. We will respond to this email with a brief description of what is involved in the study and inclusion / exclusion criteria. Our email will also instruct potential participants to simply say that yes they do or do not meet all of the screening criteria (without specifying which criteria they do / do not meet). If they say they meet all criteria, they are invited to a first session for informed consent procedures. After they give consent, they then fill out detailed screening forms which we retain as part of the study record.

Our anticipated enrollment will approximate the demographics of Piscataway and the Rutgers University community including 26 not Hispanic or Latino and 4 Hispanic or Latino participants. Racial breakdown will approximate 22 Asian, 12 Black or African American, 22 White, and 4 More than One Race participants. All participants will be between the ages of 18 and 45.

To increase the chances that participants come to all study sessions, we will describe the procedures in detail during the recruitment and consenting processes, indicating that we are recruiting participants who would be willing to participate in all sessions (though participants can, at any time, decide to no longer participate and there will be no penalty if that happens). We will also send participants a calendar invite to remind them of their participation and a reminder email the day before their session.

Participants will be paid \$20/hour for MRI, or TMS and EEG experiments. Depending on the experiment, participants may have the opportunity to earn additional compensation. Specifically, participants will have the opportunity to select among offers of money to repeat different levels of the oculomotor control tasks for money. Based on their choices, participants may receive an additional (\$0.50 to \$5.00) in each experimental TMS sessions. This bonus is part of an experimental design intended to assess how people evaluate the subjective costs of cognitive effort.

Participants in MRI are also given an anatomical picture of their brain in digital format if they desire. Participants will be paid in cash, at the end of each experimental session. For participants completing the

three sessions (MRI, active TMS, and control stimulation), their total pay will not exceed \$295 across all three sessions (\$40 for the MRI session, and \$85 each for the TMS sessions).

We do not believe these nominal amounts to be coercive and moreover will inform participants that they can end their participation in the experiment at any time, and they will receive a pro-rated amount of remuneration for their time in the respective session.

## 6 STUDY INTERVENTION(S) OR EXPERIMENTAL MANIPULATION(S)

### 6.1 STUDY INTERVENTION(S) OR EXPERIMENTAL MANIPULATION(S) ADMINISTRATION

#### 6.1.1 STUDY INTERVENTION OR EXPERIMENTAL MANIPULATION DESCRIPTION

The study intervention is modulation of cortical excitation to inhibition (E/I) balance in the right frontal eye field (FEF) by means of 2 trains of spaced continuous theta burst stimulation (cTBS) or intermittent theta burst stimulation (iTBS) using a transcranial magnetic stimulation device. As prior work (Huang et al 2005; Chung et al. 2018) has shown that cTBS reliably decreases the cortical E/I ratio with diverse cortical targets and iTBS increases the E/I ratio, we expect to replicate a reduction in E/I balance when cTBS is applied to the FEF and an increase in E/I balance when iTBS is applied. The mechanism of action is thought to be a manipulation of inhibitory neurotransmission across diverse timescales. The endpoint of this stimulation will be a modulation of the local E/I ratio that should last at least 60 minutes post-stimulation (Chung et al., 2016).

We will assess the changes in E/I balance by quantifying the functional E/I ratio as previously done in a study of the GABA receptor agonist Zolpidem (Bruining et al. 2020). We furthermore anticipate that a reduction in FEF E/I balance will also make the dynamics of FEF more sub-critical while an increase would make FEF more super-critical (Pfeffer et al. 2018; Poil et al. 2012). Thus, depending on whether participants' brains operate in a sub- or super-critical regime at baseline, we predict that cTBS and iTBS manipulations will either make their brains operate closer to or farther from criticality. If cTBS / iTBS make participants' brains operate closer to criticality, this will be reflected by an inferred functional E/I ratio of 1.0, and stronger long range temporal correlations. Conversely values farther from 1.0 will correspond with weaker long-range temporal correlations otherwise found in the brain in a critical state. Moreover, we will test the prediction that cTBS / iTBS to the FEF will affect oculomotor control. Specifically, we predict that since criticality affords maximal susceptibility and flexibility, tasks which require more stability (e.g. short term memory tasks) will be performed with less precision and more trial-to-trial variability in accuracy and reaction times at criticality. Since criticality also maximizes information transfer capacity,

performance will increase for tasks which require better inter-regional communication (e.g. top-down control tasks) when brains operate near criticality. Hence we specifically predict that TMS manipulations which make the FEF operate closer to criticality will result in worse and more variable memory-guided saccade task performance, and better and more consistent anti-saccade task performance.

Importantly, we will contrast the effects of active cTBS and iTBS with sham stimulation. The double blind procedure involves flipping over the coil so that the participants' experience is as close as possible across active and sham conditions, and the experimenter will have no way of knowing which is which (both sides of the coil are identical and flipped based on an internal blinding code within the stimulator unit) until experimental de-blinding.

#### 6.1.2 ADMINISTRATION AND/OR DOSING

As noted, the intervention is spaced, cTBS and iTBS to the right frontal eye field. Each cTBS session will thus entail two trains of 50 Hz triplet bursts of stimulation delivered at 5 Hz (theta rhythm) continuously for 40 seconds (600 pulses for each train for a total of 1200 pulses) at an intensity based on 80% of a participant's active motor threshold. iTBS will entail brief 2 s trains of 50 Hz triplet bursts of stimulation delivered at 5 Hz (theta rhythm), separated by 10 s for a total of 190 pulses (600 pulses) and, as with cTBS, this total train will be repeated twice (for a total of 1200 pulses) at an intensity based on 80% of a participant's active motor threshold. These two trains will thus constitute the full-dose at the FEF. Sham stimulation will, at random, entail either cTBS or iTBS, with the coil positioned over participants' FEF, but flipped so that it will have no effect on neuronal function.

Each participant will have their own individual set of three stimulation sessions and will thus not interact with other participants during the study.

#### 6.2 FIDELITY

##### 6.2.1 INTERVENTIONIST TRAINING AND TRACKING

All TMS operators will receive training on the two key variables which may affect the consistency of stimulation. The first is the strength of stimulation intensity. Here, stimulation intensity will be based on participants' active motor threshold, which is diagnosed with the use of TMS-evoked potentials measured by electromyography and leads attached to participants' right hand, pursuant to a single pulse to their motor cortex hand knob. Motor thresholding will be based on a semi-automated threshold detection algorithm which is given feedback about the efficacy a given pulse for eliciting a motor evoked potential of 100 microvolts from peak to trough. Thus, threshold identification should be standardized across participants, as should corresponding stimulation intensities.

The second degree of freedom is the precision of TMS targeting. For both motor threshold detection, cTBS, and iTBS, it is important to ensure precise targeting (of the hand knob and FEF for motor thresholding and rTMS, respectively). To ensure consistent targeting, we will use participant-specific structural MRI scans coupled with 3D vision-based neuronavigation systems. The neuronavigation system gives real-time feedback for precision targeting. Also, the exact location of every single pulse is recorded during stimulation, to ensure consistency in targeting.

### 6.3 MEASURES TO MINIMIZE BIAS: RANDOMIZATION AND BLINDING

All participants will complete both one sham and two active stimulation sessions, but the order of these sessions will be pseudo-randomized. Specifically, participants will be assigned participant ID numbers based on their order of recruitment, but the participant ID numbers will be pseudo-randomized with respect to double-blind-coded active versus sham stimulation. Pseudo-randomization of double-blind codes will be generated by a script and saved in a digital file. The de-blinding key to this digital file will be saved by a collaborator not directly involved in conduct of the study and will not be accessed by study personnel until the end of data collection.

The specific session that a participant is in (active versus sham stimulation) will be unknown to the experimenter since the stimulator is only set to function in active or sham stimulation model based on the double-blind codes. To maintain blinding, the experimental condition will not be explained to the participant until after the conclusion of data collection, at the participants' request.

While it may be possible for some participants to infer the distinction between active and sham stimulation, we will not discuss conditions with participants nor will we discuss with participants our predictions about how active versus sham stimulation should differentially impact oculomotor control.

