## 8 STUDY ASSESSMENTS AND PROCEDURES

### 8.1 ENDPOINT AND OTHER NON-SAFETY ASSESSMENTS

During the screening process, participants will be informed about basic inclusion / exclusion criteria after they first contact us, by email. We will then ask participants questions, by phone, on the MRI and TMS screening forms in detail and indicate whether they meet criteria or not. Although we will not yet ask participants to fill out these forms (i.e. no data will be recorded at this stage), we will ask them to confirm that they meet all criteria on the forms, prior to scheduling their first visit. Within two weeks of this confirmation, we will invite participants for their first session visit.

At the first visit, participants will complete the informed consent process and then be asked to fill out the screening forms, after giving consent. These data will include information about psychiatric or psychological history, presence or absence of metal in the body, history of physical trauma to the brain, current alcohol or drug abuse, current use of psychiatric medications, and use of other medications which may lower the seizure threshold. We will also collect basic demographic and handedness information.

Following the informed consent process the following data will be collected during the study.

- **Performance-based assessments:** Oculmotor task performance, decision-making task performance
- **Questionnaires:** The Need for Cognition Scale
- **Imaging assessments:** Using a 64-channel EEG system, we will record brain waves at the scalp throughout all procedures during the stimulation session. In the MRI scanner we will collect several types of scans. For the purposes of TMS neuro-navigation, we will collect T1 MPRAGE sequences, structural localizer scans, functional localizer scans, and a field map scan. We will also collect 10-12 minutes of resting state fMRI data. These data will be collected on a 3T MRI.

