## 9 STATISTICAL CONSIDERATIONS

There will not be a formal Statistical Analysis Plan (SAP). Also, no statistical plan will be posted publicly or registered before the study begins.

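### The key may be opened when data collection ends, so the blind is not required to cover the processing from which 15 of the 18 listed measures are derived

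*Protocol*

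**What the plan says.** Section 6.3 (Measures to Minimize Bias) says the key is kept by a collaborator not directly involved in the study and "will not be accessed by study personnel until the end of data collection".

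Section 4.1 gives the time differently: "This collaborator will maintain the blinding codes until de-blinding at the end of the study". Section 4.4 then fixes what that means: "The end of the study is defined as completion of the third stimulation session". Section 6.1.1 refers to de-blinding without a date.

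The blind is described for two parties. The participant is not told the condition, and during delivery "the experimenter will have no way of knowing which is which". No masked data processor or analyst is named.

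The raw material includes 64-channel EEG; section 8.1 says "we will record brain waves at the scalp throughout all procedures during the stimulation session". Section 9.4.2 lists the measures to be obtained.

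On pre-specification, section 9 says: "There will not be a formal Statistical Analysis Plan (SAP). Also, no statistical plan will be posted publicly or registered before the study begins". The trial itself will be registered at ClinicalTrials.gov (10.1.11).

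**The concern.** The endpoints based on recordings do not exist when the last session ends. Long-range temporal correlations, avalanche statistics, functional E/I, bistability, saccade accuracy and latency, and pupil dilation must all be computed afterwards. That takes judgement about which channels, epochs and trials to keep and how to score or fit them. Section 9.1 places the EEG effects near the stimulated target but does not say which of the 64 channels count as near. The other steps are not described in the protocol at all.

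If those choices are made with the codes known, they can drift towards the expected result without anyone intending it. The contrast at risk is active versus sham, on which the trial's causal claim rests. A locked plan would be the usual second safeguard, and section 9 rules out a formal one. Once the codes are known to the people who process the data, masking cannot be restored.

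**Working it through.** The protocol states no figure on this point, so the check is mainly a comparison of text.

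**1. Earliest permitted release.**
- 6.3: end of data collection.
- 4.1 with 4.4: end of study, meaning completion of the third stimulation session.
- 6.1.1: no date.

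Both dated rules are recording milestones. Section 4.4 can also be read participant by participant, which would be earlier still. None of these sections, nor any other, requires processing, scoring, exclusions or code to be finished first.

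**2. Measures still to be derived at that point (count from 9.4.2).**

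| Group | Listed | From EEG, saccade or pupil recordings |
|---|---|---|
| Subjective effort | 4 | 1 (pupil) |
| E/I balance | 3 | 3 |
| Critical dynamics | 3 | 3 |
| Memory-guided saccade | 4 | 4 |
| Anti-saccade | 4 | 4 |
| Total | 18 | 15 |

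The other 3 (effort ratings, indifference-point values, motivation scales) rest on responses given while the participant is blind.

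**3. What the key conceals.** Each participant has one active cTBS, one active iTBS and one sham session (4.1, 4.4), and the sham uses either pattern (6.1.2). By 4.1, cTBS runs continuously for 40 s, while iTBS comes in 2 s trains separated by 10 s, so whoever delivers it can tell them apart. Over three sessions one pattern occurs twice and the other once.
- Sham is cTBS: cTBS, cTBS, iTBS. The iTBS session is active.
- Sham is iTBS: iTBS, iTBS, cTBS. The cTBS session is active.

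The unrepeated pattern is therefore always active. The key hides only which of the two same-pattern sessions is sham.

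**4. Illustrative size.** Assumptions, none from the protocol: there is no true effect, the analyst keeps the most favourable of k defensible pipelines, and the k test statistics are standard normal with common correlation ρ. With critical value c, density φ and distribution function Φ, the two-sided error is

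1 − ∫ φ(u) [Φ((c − √ρ·u)/√(1−ρ)) − Φ((−c − √ρ·u)/√(1−ρ))]^k du.

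At c = 1.96 (5% per test, uncorrected):
- k = 3, ρ = 0.9: 8.4%
- k = 5, ρ = 0.9: 10.2%
- k = 5, ρ = 0.7: 14.8%

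Simulation of the same model gives 8.4%, 10.1% and 14.8%.

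Section 9.4.1 promises a multiplicity correction without naming it. If it were Bonferroni over 18 measures (assumed), the nominal level is 0.05/18 = 0.28% per outcome. The same formula then gives 0.70% (k = 5, ρ = 0.9) and 1.05% (k = 5, ρ = 0.7). The absolute error is small, but it is still about 2.5 to 3.8 times nominal.

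**The case against.** **The protocol does not say that processing will be unblinded.** This stands. Section 6.3 sets the earliest time for opening the key, and the team may well process first. A reader might infer that unblinded processing is planned, or that the double-blind label is contradicted. Neither follows, because the label is described for participant and experimenter and both are covered. What remains is that the section on minimizing bias sets a release time too early to protect the derived outcomes.

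**Other provisions limit the analyst.** This stands in part. Section 9.4.2 names the measures, the regression form, the covariates and the type of correlation. Section 9.4.1 sets p < 0.05 with correction for multiple comparisons, 9.3 includes all participants, and 9.4.8 commits to reporting individual values. So one cannot say that nothing else guards against selective analysis. But none of these fixes channel choice, epoch or trial rejection, scoring or fitting, and a correction across reported tests does not reach pipelines that were tried and dropped.

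**The trial will be registered.** True (10.1.11). Section 9 excludes advance posting or registration of a statistical plan only, so it would be wrong to say that nothing is registered. The protocol does not say that the registry entry will carry processing rules.

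**Such detail belongs in an SAP.** That would normally answer the point. Here the protocol says there will be no formal SAP, and the release rule is a protocol provision in any case.

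**The error figures are invented.** Fair, as far as k and ρ go. They describe deliberate selection and serve only as an upper illustration.

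**Conclusion.** The point holds in a limited form: as written, the blind is not required to extend over the derivation of 15 of the 18 listed measures, and no formal plan is promised to fix those choices beforehand. This rests on the text of 4.1, 4.4, 6.3, 9 and 9.4.2. The only outside inference is that EEG, saccade and pupil outcomes need judgement-laden processing after the session.

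The size is unknown. The range of 8% to 15% is a worst case under assumed k and ρ, before multiplicity correction. It does not forecast this team's conduct and is not the planned error rate.

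A reader might also infer that opening the key reveals all three conditions at once, so that delaying release would by itself mask the processing. The documents do not support that. The pattern is apparent to operators and already identifies one active session per participant, so later release protects fully only if pattern and order are also kept from those who process the data.

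The change should be made before the first unblinding. The weakness is not fatal to the design.

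**What to change.** In 6.3 and 4.1, replace the release condition with wording to this effect:

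- The collaborator releases the key only after (a) EEG preprocessing, saccade and pupil scoring, and all trial, session and participant exclusions are complete, and the derived dataset is frozen under masked session codes; and (b) the analysis scripts are dated and locked. Later changes are reported as post-unblinding.
- Where feasible, pulse pattern and session order are withheld from those processing the data. If the EEG files run through the stimulation itself, as 8.1 suggests, that segment should be removed before the files are passed on. Session order, which 4.1 makes a covariate, can be merged after the freeze.
- The end-of-study definition in 4.4 does not trigger release of the key.

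The cost is a few sentences of protocol text, minor file recoding, and a wait until the freeze before staff see the conditions. If the same people deliver stimulation and process the data, masking of the pattern will be incomplete, and the report should say so. An outside collaborator already holds the key, so no participant, visit or key-holding role is added.
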